8.2 Subgroup Definition and Parameterization

Not applicable.

9 General Specifications for Data Analyses

The results of this study will be reported using summary tables, figures, and data listings, as appropriate. All data will be summarized by study intervention and/or scheduled time point, as applicable.

Listings

In the individual participant data listing all individual data will be listed as measured. Repeated and unscheduled measurements will be included in the listings. All listings will be sorted by subject ID and nominal time point, if not stated otherwise.

Tables and Descriptive Statistics

All safety data will be summarized overall and study intervention by nominal time point, as appropriate. All PK data will be summarized by study intervention and nominal time point. Repeated and unscheduled measurements included in the listings will not be used for statistical analyses or summaries, unless the repeated measurement was performed due to unreliable values/technical reasons, e.g., clotted samples.

Unless otherwise specified, continuous variables will be summarized using descriptive statistics, i.e. the number of participants with non-missing values (n), the number of participants with missing values (nmiss), mean, standard deviation, median, 25th percentile (Q1) and 75th percentile (Q3), minimum, and maximum. If there are no missing values the number of participants with missing values should be indicated by a 0. Mean, Median, Q1, Q3, Min, Max will have the same precision as the SDTM data (decimal places). SD will be presented with one decimal place more than the mean.

Qualitative variables will be summarized by frequency counts and percentages. Unless otherwise stated the calculation of proportions will be based on the number of participants of the analysis set of interest that received the respective study intervention for safety, QTc and PK summaries and for all other evaluations the analysis set of interest [N]. Therefore, counts of missing observations will be included in the denominator and presented as a separate category.

Study day 1 for this study is defined as the start date of study intervention.

The following labels will be used for the study interventions in all tables, graphs and listings, if not stated otherwise:

| | |
|----------------------|-----------------------------|
| Placebo: | Placebo |
| 400 mg Moxifloxacin: | 400 mg Moxifloxacin tablet |
| 45 mg Evobrutinib: | 45 mg Evobrutinib solution |
| 225 mg Evobrutinib: | 225 mg Evobrutinib solution |

All statistical analyses will be performed using SAS® Software version 9.2 or higher and R version 4.1 or higher.

9.1 Definition of Baseline and Change from Baseline

If not otherwise specified, 'baseline' refers to the last scheduled measurement before administration of study intervention in each period.

However, if a participant is missing the baseline collection, the previous non-missing evaluation could become the baseline value (e.g. from Screening). If no baseline or previous to baseline evaluations exist, then the baseline value will be treated as missing.

For the ECG measurements, 'baseline' refers to the average of the derived ECG intervals from the three ECG timepoints prior to dosing on day 1 within each respective period.

Absolute changes from baseline are defined as

$$\text{absolute change} = \text{visit value} - \text{baseline value}$$

9.2 Study Day / Study Intervention Day

Day 1 is the day of start of study intervention, the day before is Day -1 (no Day 0 is defined). Study day is defined relative to Day 1.

9.3 Definition of Duration and ‘Time Since’ Variables

The following definitions and calculations of duration, as applicable, will be applied:

- Duration of AE (in days hh:mm) = end date and time - start date and time of the AE, if missing time for either the beginning or end then = end date – start date + 1; in case of multiple records for the same AE, the duration will be calculated over all these records
- Days hh:mm from dosing (onset post administration) = start date and time of the event - date and time of last dose administration of study intervention (calculated for each intervention, for TEAEs), if missing time for either the dosing or event then days hh:mm from dosing = event start date – date of dose administration + 1
- Relative (Rel.) Day in period of AE = start date of the event – date of admin in period + 1 (for AEs on or after the day of dosing within a period)
- Relative Day in study of AE = start date of the event – date of first admin + 1 (for AEs on or after the first day of dosing)
- Rel. Day in study of AE = start date of the event – date of first admin (for events before the first day of dosing of the study only)

9.4 Imputation of Missing Data

In this Phase I thorough QT study, missing observations will be assumed to be missing completely at random (MCAR) if not stated otherwise. No action will be taken to handle missing data. A participant who withdraws prior to the last planned observation in a study period will be included in the analyses up to the time of discontinuation.

10 Study Participants

The subsections in this section include specifications for reporting participant disposition and study intervention/study discontinuations. Additionally, procedures for reporting protocol deviations are provided.

10.1 Disposition of Participants and Discontinuations

The following will be presented in a summary table:

- Total number of participants screened (i.e., participants who gave informed consent)
- Number of screened participants who discontinued from the study prior to first dosing overall and grouped by the main reason for discontinuation:
 - Participant did not meet all eligibility criteria

- Withdrew consent
- Other (e.g., COVID-19-related and COVID-19-non-related)
- Number of treated participants
- Number and percentage of treated participants who completed study
- Number and percentage of treated participants who discontinued the study or study intervention, with the primary reason of discontinuation:
 - Adverse event
 - Lost to follow-up
 - Protocol non-compliance
 - Death
 - Withdrew consent
 - Other (e.g., COVID-19-related and COVID-19-non-related)

The number and percentage of participants will be presented by group of study intervention and total, where applicable. Percentages will be presented with respect to the number of treated participants, where applicable.

A listing of discontinued participants will be provided.

A listing of participants affected by the COVID-19 related study disruption by unique participant identifier will also be provided.

10.2 Protocol Deviations / Exclusion from Analysis Sets

10.2.1 Important Protocol Deviations

Listings of important protocol deviations will be provided including the date and relative day in relation to dosing in the relevant period. A distinction will be made between important protocol deviations due to COVID-19 versus not due to COVID-19. The respective important protocol deviations will be flagged accordingly.

Important protocol deviations or important events that might influence PK and QTcF analysis include, but may not be limited to the following:

- Adverse events, diarrhea etc. (these instances will be discussed on a case-by case basis)
- Vomiting after administration following oral dosing (these instances will be discussed in alignment with applicable regulatory guidelines on a case-by-case basis)
- Sample processing errors that may lead to inaccurate bioanalytical results
- Inaccurate dosing or dosing errors (e.g., dose administration delayed, dose change or missed doses)

- Predose or trough sample collected after the actual dosing
- Non-compliance with food and drink requirements (e.g., non-fasted, incomplete meal consumption, caffeine intake)
- Concomitant medication, vitamins, dietary or herbal supplements
- Missing baseline Holter ECG in triplicate or post-baseline Holter ECG in triplicate

Should one or more of these events be available at the Data Review Meeting, its implication for PK and QTcF evaluation will be discussed and agreed amongst relevant study team members (e.g., Sponsor Clinical Pharmacology/Biostatistics/Clinical Pharmacokinetics & Pharmacodynamics team/Pharmacometrics representative). Appropriate action will be taken such as flagging individual values to be excluded from analysis.

10.2.2 Reasons Leading to the Exclusion from an Analysis Set

If participants are excluded from the PK Analysis Set and/or ECG Analysis Set, the reasons for exclusion will be listed.

Reasons for excluding individual PK concentrations from PK analysis as well as C-QTc analysis will also be listed separately and flagged in the main listing.

11 Demographics and Other Baseline Characteristics

Demographics and baseline characteristics will be presented for the SAF.

11.1 Demographics

Descriptive statistics will be presented for age, height, weight, and BMI. Frequency counts and percentages will be presented for sex, race, and ethnicity. The summary will be performed overall.

BMI (kg/m²) will be derived (i.e., not taken directly from the database) according to the following formula:

$$\text{BMI [kg/m}^2\text{]} = \frac{\text{weight [kg]}}{\text{height[cm}^2\text{]}} \times 10000$$

11.2 Medical History

Medical history will be coded using the MedDRA, most current version at time of data base lock, and listed.

The medical history will be listed by participant including PT as event category and SOC body term as Body System category.

11.3 Other Baseline Characteristics

Other baseline measurements, such as virus screen, alcohol and drugs of abuse screen, pregnancy test in women, nicotine, and alcohol consumption, will be listed.

Baseline characteristics with respect to vital signs, physical examinations, and hematology/biochemistry will be part of Section 15 (Safety Evaluation).

12 Previous or Concomitant Therapies/Procedures

Medications will be presented for the Safety Analysis Set.

Previous medications are defined as any medication discontinued prior to the administration of study intervention. Concomitant medications are defined as any medication taken during the course of the study, with a starting date greater than or equal to the administration of study intervention, or with a starting date prior to the administration of study intervention and ongoing at the time of the administration of study intervention.

The World Health Organization Drug dictionary most current version at time of database lock, will be used for coding of prior and concomitant medications and they will be described using PT as applicable.

Previous and concomitant medications will be listed. Concomitant procedures, if any, will also be listed.

13 Study Intervention: Compliance and Exposure

The dosing of each participant is monitored by the study nurse or investigator. A listing of date and time of each drug administration and each blood sampling, including time deviations as well as measured plasma concentrations, will be provided sorted by participant. Information on meal intake will be listed by participant, if provided.

14 Efficacy Analyses

Not applicable.

15 Safety Analyses

This section includes specifications for summarizing safety endpoints that are common across clinical studies such as adverse events, laboratory tests and vital signs.

All safety analyses will be performed for the Safety Analysis Set and will be presented by study intervention and nominal timepoint, as appropriate.

Safety analyses will be done according to the as-treated principle.

15.1 Adverse Events

All AEs recorded during the study will be coded with the MedDRA, latest version at time of database lock, and assigned to a SOC and a PT.

TEAEs are those events with onset dates on or after the first administration of study intervention on Day 1. Any AE occurring before the administration of study intervention on Day 1 and resolved before administration of study intervention or not worsening after administration of study intervention on Day 1 will be included in the AE listings but will not be included in the summary tables (unless otherwise stated). These will be referred to as "pre-treatment" AEs.

In case AE-related dates are partial, the available information will be used in a conservative approach to determine whether the AE is treatment-emergent.

All analyses described in Section 15.1 will be based on TEAEs if not otherwise specified. The AE listings will include all AEs (whether treatment-emergent or not). AEs outside the on-treatment period will be flagged in the listings.

Unless otherwise specified, TEAEs will be summarized, by number and percentage of participants with the TEAE in the category of interest, as well as the number of events, in total by primary SOC and PT in alphabetical order for SOC and decreasing overall frequency for PT.

If an event was reported more than once due to change in intensity and change in relationship, the worst severity and the worst relationship to study intervention will be tabulated.

Each participant will be counted only once within each SOC or PT.

15.1.1 All Adverse Events

TEAEs and participants experiencing TEAEs will be summarized by study intervention and overall with:

- The number and percentage of participants with any TEAE, any related TEAE, any serious TEAE, any related serious TEAE, any severe TEAE, any related severe TEAE, any AESI, any TEAE leading to death, any related TEAE leading to death, any TEAE leading to study discontinuation

- The number and percentage of participants with at least one TEAE and the number of events by SOC and PT.
- The number and percentage of participants with TEAEs excluding SAEs and the number of events, with frequency $\geq 5\%$ in any study intervention arm by SOC and PT
- The number and percentage of participants with at least one TEAE and the number of events by severity, SOC, and PT
- The number and percentage of participants with at least one related TEAE, evobrutinib-related TEAE, moxifloxacin-related TEAE, and placebo-related TEAE and the number of events by SOC and PT
- The number and percentage of participants with at least one AESI recorded and the number of events by SOC and PT.

Unless otherwise stated, AEs will be displayed with SOC terms sorted alphabetically and PTs within each SOC term sorted in descending overall frequency.

For determining incidence counts, within each level of TEAE term, if a participant experiences more than one occurrence, the participant will only be counted once for that TEAE.

AEs related to any study intervention are those events with relationship missing, unknown or yes.

In case a participant had events with missing and non-missing severity, the maximum non-missing severity will be displayed.

15.1.2 Adverse Events Leading to Discontinuation of Study Intervention

A listing of TEAEs leading to discontinuation of study intervention, or discontinuation of study, if any, will be provided.

The frequency (number and percentage) of participants with TEAEs leading to permanent discontinuation of each study intervention by study intervention will also be provided in a table.

15.2 Deaths, Other Serious Adverse Events, and Other Significant Adverse Events

15.2.1 Deaths

A listing of deaths, if any, will be provided.

15.2.2 Serious Adverse Events

A listing of SAEs, if any, will be provided.

Summary table of the number and percentage of participants with at least one SAE by SOC and PT will also be provided.

15.2.3 Other Significant Adverse Events

The following AESI were defined:

- Infections (serious, severe, and opportunistic, \geq Grade 3)
- Seizures
- Elevated lipase, elevated amylase, pancreatitis
- Liver-related events

More information can be found in the CSP, Section 8.3.7.

AESIs will be flagged based on an external excel file which includes the precise descriptions of the AESIs (SMQs, PTs and laboratory constellations) and will be used to retrospectively identify AESIs in the AE listings. Summary table of the number and percentage of participants with at least one AESI by SOC and PT will also be provided.

In addition to the AESIs defined above, the preferred term including “Syncope” or “Pre-syncope”, if any, will also be flagged and summarized.

15.3 Clinical Laboratory Evaluation

Listings and summary statistics at each assessment time will be presented using SI units. Normal ranges will be provided by the laboratory department, and out of range flags will be calculated based on the normal ranges. Laboratory data not transferred from the central laboratory in SI units will be converted to SI units before processing. Both original units and SI units will be provided in the SDTM domain.

Safety laboratory parameters are separated into:

- Hematology (including coagulation)
- Biochemistry
- Urinalysis
- Other tests

Hematology (including coagulation) and biochemistry will be summarized by treatment and time point using descriptive statistics.

Listings of abnormal test results (low and high) will also be provided.

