1.3 Schedule of Activities

Assessments & Procedures	Screening	Treatment												Safety Follow-up call	Comments
		P1			P2			P3			P4				
Study Day(s)	-28 to -2	-1	1	2	7 ^a	8	9	14 ^a	15	16	21 ^a	22	23 ^b	29	^a Assuming 7 days washout between treatment periods. ^b End of Treatment assessment.
Period-specific Day(s)	-28 to -2	-1	1	2	-1	1	2	-1	1	2	-1	1	2		
Informed consent	X														Prior to any screening activity
Participants resident at CRU		X	X	X	X	X	X	X	X	X	X	X	X		Discharge on Day 2 of each period
Eligibility criteria	X	X ^c			X ^c			X ^c			X ^c				^c Recheck of health status on Day -1.
Demography, height & weight	X														Demography to include, at minimum age (year of birth), sex, race, and ethnicity.
Medical history	X														
Serum pregnancy test	X	X			X			X			X				
Viral serology, TSH, eGFR, QuantiFERON® test	X														
Cotinine, alcohol and drugs of abuse testing, SARS-CoV-2	X	X			X			X			X				
Randomization			X												
Physical examination	X	X			X			X			X		X		Brief examination on Days -1 of each period to recheck eligibility/ healthy state after return to CRU and on the End of Treatment assessment visit.
Vital signs	X ^d	X	X ^d	X	X	X ^d	X	X	X ^d	X	X	X ^d	X ^d		Vital signs will be assessed on Day -1 of each period and on the days of dosing (Day 1 of each period) at predose and 1, 2, 6, and 24 h postdose. ^d Body temperature will be assessed at Screening, predose, and the End of Treatment assessment visit. At visits where assessment time points coincide with each other, the following sequence of activities will be followed: safety ECG followed by vital signs within 30 minutes before the specified time point preceding the PK sampling, which will be performed at the specified time point.
Safety ECGs	X		X		X			X			X				Safety ECG at 2 h postdose in each period.

Assessments & Procedures	Screening	Treatment												Safety Follow-up call	Comments
		P1		P2		P3			P4						
Study Day(s)	-28 to -2	-1	1	2	7 ^a	8	9	14 ^a	15	16	21 ^a	22	23 ^b	29	^a Assuming 7 days washout between treatment periods. ^b End of Treatment assessment.
Period-specific Day(s)	-28 to -2	-1	1	2	-1	1	2	-1	1	2	-1	1	2		
Holter recordings			X	X		X	X		X	X		X	X		Holter recordings starting 1 hour prior to first timepoint on Day 1 and lasting at least until last timepoint of PK sampling on Day 2 (24 h postdose) of each period.

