Triplicate ECGs from Holter recordings			X	X		X	X		X	X		X	X		On each dosing day 12-lead ECGs extracted in triplicates from Holter recordings at 3 timepoints before dosing (-1 h, -30 min, and -10 min), and at 15 and 30 min and 1, 1.5, 2, 2.5 3, 4, 6, 8, 12, 16 h and at 24 h postdose.
Clinical laboratory safety tests	X	X			X			X			X		X		Blood samples for the clinical laboratory safety assessments will be collected in a fasted condition.
PK sampling (evobrutinib, evobrutinib major metabolite, and moxifloxacin)			X	X		X	X		X	X		X	X		Plasma samples for PK analysis will be collected on the days of dosing (i.e., Days 1, 8, 15, and 22) at predose and 15 and 30 min, and 1, 1.5, 2, 2.5, 3, 4, 6, 8, 12, 16 and 24 h postdose. At visits where assessment time points coincide with each other, the following sequence of activities will be followed: PK sample to be collected shortly (within time windows specified) after ECG.
Study intervention administration			X			X			X			X			
Previous/concomitant medication monitoring	X	<=====>													Section 6.8.
AE monitoring	X	<=====>													Section 8.3.

CRU=clinical research unit; ECG=electrocardiogram; eGFR=estimated glomerular filtration rate; FSH=follicle stimulating hormone; PK=pharmacokinetics; SARS-CoV-2=severe acute respiratory syndrome coronavirus 2; TSH=thyroid stimulating hormone.

2

[figure not shown]
Introduction

Evobrutinib is an oral, selective, irreversible inhibitor of BTK that is in clinical development for the treatment of autoimmune diseases, e.g. RMS. Detailed information on the chemistry, pharmacology, efficacy, and safety of evobrutinib is in the current IB.

This study is being conducted to assess potential effects of evobrutinib on cardiac repolarization (i.e., prolongation of QT interval).

CC1

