2.3.3 Overall Benefit: Risk Conclusion

Risk minimization measures routinely implemented in early phase clinical studies are considered adequate, including exclusion criteria (see Sections 5.1 and 5.2), adequate biochemical and hematology laboratory monitoring (see Section 8.2.4), and observation of vital signs and ECGs (see Sections 8.2.2 and 8.2.3). Participants will be admitted to the study site for the duration of the study to allow continuous safety monitoring. Considering the measures taken to minimize risk to participants in this study, the potential risks identified in association with evobrutinib and moxifloxacin are justified in healthy participants.

3 Objectives and Endpoints

Objectives	Endpoints	Ref. #
Primary		
To evaluate whether evobrutinib administered as a single oral dose (as solution) of 45 mg or 225 mg prolongs QT/QTc in comparison to placebo control	ΔΔQTcF (placebo-corrected change from baseline QTcF) for evobrutinib; with concentration-QTc analysis as primary analysis	1
Secondary		
To demonstrate QTc assay sensitivity	ΔΔQTcF (placebo-corrected change from baseline QTcF) for moxifloxacin	2
To assess the safety and tolerability of evobrutinib	Nature, occurrence, and severity of TEAEs Absolute values and changes in safety laboratory tests Vital signs assessed from time of first dose to end of study participation Single 12-lead ECGs evaluated by Investigator	3
To assess the effect of evobrutinib on other ECG parameters	QT, QTcB, QTcl, PR, QRS, RR, HR, cardiologist assessment including T-wave morphology, and U-wave.	4
To determine the PK of evobrutinib and its major metabolite at 45 mg and 225 mg oral dose (solution) under fasting conditions and moxifloxacin at 400 mg oral dose	AUC ₀₋₂₄ , AUC _{0-∞} , C _{max} , and t _{max} for evobrutinib and major metabolite AUC ₀₋₂₄ , AUC _{0-∞} , C _{max} , and t _{max} for moxifloxacin	5

4 Study Design

This is a Phase 1, single-center, randomized, double-blinded, placebo- and positive-(moxifloxacin) controlled, single-dose, 4-period crossover thorough QT study. There will be a at least 7-day washout period between successive doses. **CCI**

Eligible participants will be randomized to 1 of 4 treatment sequences in which each of the 4 treatments will be administered sequentially during 4 treatment periods. The 4 treatments are:

- Therapeutic dose, double-blind: single oral dose of evobrutinib (45 mg) solution, administered under fasted conditions;

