9.4.1 Safety Analyses

All safety analyses will be performed on the Safety Analysis set.

Reference #	Endpoint	Statistical Analysis Methods
Primary		
Not applicable		
Secondary		
3	Nature, occurrence, and severity of TEAEs	AE counts and participants with Aes will be summarized for each treatment by SOC and PT. In addition, Aes will be tabulated and listed per participant and analyzed by severity and relationship to study intervention.
3	Absolute values and changes in safety laboratory tests	Safety laboratory parameters will be listed for each participant including flags for measurements outside the reference ranges, where applicable. Laboratory parameters (hematology and clinical chemistry) will be summarized by time point including absolute values.
3	Vital signs assessed from time of first dose to end of study participation	Vital signs by participant, including changes from Baseline, will be listed and summarized by treatment and time point using descriptive statistics.
3	Single 12-lead ECGs evaluated by Investigator	Electrocardiogram data will be summarized by absolute values and changes from Baseline values by treatment using descriptive statistics. Clinical noteworthy ECG findings for individual participants will be listed and summarized as appropriate.

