15.4 Vital Signs

Vital signs data will be summarized by treatment and time point using descriptive statistics for baseline (see definition in Section 9), each evaluation during the study, and change from baseline to each evaluation. Listings of vital sign data will be provided.

Vital sign summaries will include all vital sign assessments from the on-treatment period. All vital sign assessments will be listed, and those collected outside the on-treatment period will be flagged in the listing.

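### SAP 15.3 plans no change summary for safety labs although endpoint 3 names changes, and the only lab sample after each period 1–3 dose is tabulated solely as the next treatment's baseline

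*SAP*

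**What the plan says.** **Endpoint.** Protocol Section 3 and SAP Section 5 both give the laboratory part of secondary endpoint 3 as "Absolute values and changes in safety laboratory tests".

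**Analysis.** Protocol 9.4.1 states: "Laboratory parameters (hematology and clinical chemistry) will be summarized by time point including absolute values". SAP 15.3 states: "Hematology (including coagulation) and biochemistry will be summarized by treatment and time point using descriptive statistics". SAP 15.3 also plans listings, out-of-range flags and listings of abnormal results. Neither section mentions a change from baseline. For vital signs, SAP 15.4 covers baseline, "each evaluation during the study, and change from baseline to each evaluation".

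**Baseline.** SAP 9.1 says that baseline, unless otherwise specified, "refers to the last scheduled measurement before administration of study intervention in each period". It defines absolute change as the visit value minus the baseline value, but ties this to no laboratory table.

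**Sampling.** In the Schedule of Activities (protocol 1.3), the row "Clinical laboratory safety tests" is marked at Screening, on Day -1 of each of the four periods, and on Day 2 of period 4. The study days are laid out "Assuming 7 days washout between treatment periods".

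**The concern.** There are two linked gaps.

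First, half of a named endpoint component has no planned output. A general formula for change is not a table, and the neighbouring vital signs section shows how the SAP words such a summary when it intends one.

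Second, no lab sample is drawn after dosing within periods 1 to 3. The first sample after each of those doses is the Day -1 sample of the next period, which the baseline rule assigns to the next treatment. Adding the missing change summary alone would therefore yield a change only for whichever treatment a participant receives in period 4.

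What is at stake is the ability to see a group-level shift by treatment. Individual values beyond limits are picked up elsewhere. A modest average shift that stays inside the normal range, or below the AESI thresholds in protocol 8.3.7 (for example transaminases above 3 × ULN, lipase or amylase above 2 × ULN), would be seen mainly in the descriptive table. Elevated transaminases are the identified risk of evobrutinib in protocol 2.3.1, although that section adds that they have not been observed in healthy participants after a single dose.

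**Working it through.** The plan gives no figure to reproduce, so the check is a count from the schedule and the sequences.

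**Inputs**
- On-study lab samples (protocol 1.3): study days -1, 7, 14, 21 (Day -1 of periods 1 to 4) and 23 (period 4 Day 2), so 5 per completer.
- Dosing (protocol 1.3): study days 1, 8, 15 and 22, if the washout is exactly 7 days.
- Sequences (protocol 6.3.1): A-B-C-D, B-D-A-C, C-A-D-B, D-C-B-A.

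**Step 1. First lab sample after each dose**

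| Dose | Next lab sample | Interval | Role under SAP 9.1 |
|---|---|---|---|
| Period 1, day 1 | day 7 | 7 − 1 = 6 days | baseline of period 2 |
| Period 2, day 8 | day 14 | 14 − 8 = 6 days | baseline of period 3 |
| Period 3, day 15 | day 21 | 21 − 15 = 6 days | baseline of period 4 |
| Period 4, day 22 | day 23 | 23 − 22 = 1 day | post-dose, period 4 |

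The washout is at least 7 days, so 6 days is the minimum for the first three rows.

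**Step 2. Coverage as the SAP stands**
- Sequence-by-period cells: 4 × 4 = 16.
- Cells with a post-dose lab value under their own treatment: period 4 only, so 4 of 16 = 25%, or 1 of 4 exposures per completer.
- The period 4 treatments across the sequences are D, C, B and A. Each treatment's post-dose row therefore comes from one sequence of four.

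**Step 3. Coverage if the next Day -1 sample is also shown under the preceding treatment**
- Periods 1 to 3: 4 × 3 = 12 cells at about 6 days or more, with change = Day -1 value of the next period − Day -1 value of the dosing period.
- Period 4: 4 cells at about 24 hours, with change = Day 2 value − Day -1 value of period 4.
- Total: 12 + 4 = 16 of 16, so each completer exposure has one value and one change.
- Coverage at about 24 hours stays at 4 of 16.

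**The case against.** The strongest reply is that the SAP already settles where a Day -1 sample belongs. SAP 9.1 makes it the baseline of its own period, SAP 9 tabulates safety data at nominal times, and the schedule labels the day as -1 within each period. This stands. A reader might infer that the treatment label of these samples is left open between two equal readings, but the documents do not support that: there is a default, and nothing suggests the alternative. What remains is that the default leaves the period 1 to 3 exposures with no lab follow-up under their own treatment.

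A reader might also infer that the SAP departs from the protocol, or that changes are ruled out. Neither holds. Protocol 9.4.1 omits changes too, and its wording includes absolute values without limiting the summary to them. The mismatch is between the endpoint and both analysis sections.

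It can fairly be said that the 1 in 4 figure reflects the sampling schedule, and that a value 6 days after a drug with a median half-life of about 2 hours (protocol 2.2) is no substitute for a 24-hour value. Both points stand. They are the reason for labelling the values and not pooling them. They do not justify leaving the only follow-up sample out of the preceding treatment's table.

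Finally, a reader might infer that safety signals would be lost. The documents do not support this. Clinically significant lab changes are recorded as AEs (protocol 8.2.4), the onset of TEAEs is timed from the last dose (SAP 9.3), and TEAEs and AESIs are summarised by study intervention (SAP 15.1.1), with laboratory constellations used to flag AESIs (SAP 15.2.3).

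**Conclusion.** The point holds as a minor, cheaply corrected gap. Part of a named secondary endpoint has no planned summary. Followed as written, the by-treatment lab table gives a post-dose value for 1 of 4 exposures per completer, although samples already scheduled would give one for all 4. The counts assume completers; the 6-day figure assumes a washout of exactly 7 days and is longer otherwise.

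The effect is confined to descriptive laboratory tables. The C-QTc analysis and the assay sensitivity assessment are unaffected, and nothing here claims that lab effects carry over between periods.

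**What to change.** In SAP 15.3:

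1. Add a change-from-baseline summary for hematology and biochemistry, using the definition in SAP 9.1.
2. State that the Day -1 sample of periods 2 to 4 is the baseline of its own period. Also show it, clearly labelled, as the end-of-washout value of the preceding treatment (about 6 days or more after that dose), with the change from the preceding period's Day -1 value.
3. Keep the period 4 Day 2 value (about 24 hours) in a separate row, and do not pool it with the end-of-washout values.

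The cost is a short SAP rule, one derived variable and one added summary, with no additional blood sampling. The drawback is a little programming and that some values appear in two labelled roles. The change does not improve coverage at about 24 hours, which stays at 1 of 4 exposures.
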